## SECTION V: RESEARCH PLAN

1. **Statement of Purpose:** State the scientific aim(s) of the study, or the hypotheses to be tested.

The specific aims with respect to increasing uptake of effective counseling and medications for tobacco, alcohol and opioid use disorders (addiction treatments) in four HIV clinics are:

**Aim 1.** Among key stakeholders, to use quantitative and qualitative (mixed) methods to identify the site-specific evidence, context and facilitation-related barriers and facilitators to the integration of addiction treatments to help tailor an Implementation Facilitation for each clinic.

**Aim 2.** To evaluate the impact of Implementation Facilitation on:

2a: Organizational readiness to deliver addiction treatments

2b: Provider readiness to deliver addiction treatments

2c: Provision of addiction treatments

2d: Changes in organizational models of care used to deliver addiction treatments

**Aim 3.** To evaluate the impact of Implementation Facilitation on ART receipt, viral suppression, VACS Index, and retention in HIV care among patients eligible for addiction treatment.

2. **Background:** Describe the background information that led to the plan for this project. Provide references to support the expectation of obtaining useful scientific data.

**Why focus on tobacco, alcohol and opioid use disorders?** These disorders are prevalent in HIV clinics, often co-occur, and effective counseling and medication treatments exist.

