**Table 5. Summary of Study Assessments**

Assessment	Data Source	Baseline Control	6 months Evaluation	12 months Maintenance
Organizational Readiness to Change Assessment	Provider and Organizational representatives	X	X	X
Change Rulers for each medication and counseling intervention	Provider and Organizational representatives	X	X	X
Conduct of screening for each condition	Electronic Medical Record	X	X	X
Use of each medication and counseling intervention	Electronic Medical Record	X	X	X
Patient demographic information	Electronic Medical Record	X	X	X
Receipt of antiretroviral therapy	Electronic Medical Record	X	X	X
Tobacco, Alcohol and Opioid Use Disorders	Electronic Medical Record	X	X	X
Psychiatric Diagnoses	Electronic Medical Record	X	X	X
Clinic Visits	Electronic Medical Record	X	X	X
Laboratory values	Electronic Medical Record	X	X	X
Receipt of benzodiazepines	Electronic Medical Record			X
Receipt of COVID-19 screening and COVID-19 diagnosis	Electronic Medical Record			X

Adequacy of sample size

Based on prior work, we anticipate that Implementation Facilitation will increase the proportion of eligible patients provided addiction treatment by the clinics from a baseline of 15% of eligible patients (Table 3) to 26% during the evaluation phase and 33% during the maintenance phase. This reflects an 11% absolute increase (75% relative increase) during the evaluation phase and a 19% absolute increase (125% relative increase) during the maintenance phase. A parallel group design, unadjusted for clustering and repeated measures would require a sample size of 592 (296 in each the control and intervention arms) to detect the estimated effect size (15% control vs. 26% intervention; power 90% and Type I error (alpha) of 0.05). We used the formula of Woertman et al. to incorporate the effect of the stepped wedge design. It was assumed that each clinic would provide a minimum of 300 addiction treatment eligible patients (n). In addition, the following assumptions were used, intracluster correlation,  $\rho = 0.01$ , number of steps,  $k = 4$ , number of baseline measurements,  $b=1$ , number of measurements taken after each

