step,  $t=1$ . With the above assumptions, the derived  $DE_{sw} = 0.63$ , thus yielding an adjusted sample size of 375 across the 4 clinics. This yields a sample size for the initial evaluation phase of 94 patients per clinic who are eligible for addiction treatment (tobacco, alcohol or opioid use disorder). Three primary time points will be used, control (six months) evaluation (six months) and maintenance (six months). Given we will have adequate power to detect a difference of a 11% increase in the provision of addiction treatments in the evaluation phase, we will be adequately powered for the 19% increase anticipated during the maintenance phase and for the other quantitative analyses proposed in Aims 2 and 3. This sample size estimated above is based on a ‘cross-sectional’ design. Even if the population in the clinics/clusters is assumed to be a stable ‘cohort’, the power will likely be more than sufficient due to within-patient correlation.

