### 3. Genetic Testing N/A

#### A. Describe

- i. the types of future research to be conducted using the materials, specifying if immortalization of cell lines, whole exome or genome sequencing, genome wide association studies, or animal studies are planned
- ii. the plan for the collection of material or the conditions under which material will be received

- iii. the types of information about the donor/individual contributors that will be entered into a database
  - iv. the methods to uphold confidentiality
- B. What are the conditions or procedures for sharing of materials and/or distributing for future research projects?
- C. Is widespread sharing of materials planned?
- D. When and under what conditions will materials be stripped of all identifiers?
- E. Can donor-subjects withdraw their materials at any time, and/or withdraw the identifiers that connect them to their materials?
- i. How will requests to withdraw materials be handled (e.g., material no longer identified: that is, anonymized) or material destroyed)?
- F. Describe the provisions for protection of participant privacy
- G. Describe the methods for the security of storage and sharing of materials

4. **Subject Population:** Provide a detailed description of the types of human subjects who will be recruited into this study.

Participants for patient focus groups will be an estimated 24-30 HIV-infected men and women with a history of tobacco, alcohol or opioid use disorder who receive care in one of the three HIV clinics. These individuals will participate in focus groups to determine their perspective on the optimal ways to integrate treatment for tobacco, alcohol and opioid use disorders into HIV clinics. We will also enroll an estimated 240 staff (clinicians and administrators) across the four sites to participate in focus groups and complete on-line quantitative assessments.

5. **Subject classification:** Check off all classifications of subjects that will be specifically recruited for enrollment in the research project. Will subjects who may require additional safeguards or other considerations be enrolled in the study? If so, identify the population of subjects requiring special safeguards and provide a justification for their involvement.

- |  |  |  |
|--|--|--|
|  Children              |  Healthy                           |  Fetal material, placenta, or dead fetus |

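### The sample size section extends adequate power to every other quantitative analysis in Aims 2 and 3, but calculates it for treatment provision only; nothing in the plan supports the extension

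*Combined protocol and SAP*

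**What the plan says.** Section V, Adequacy of sample size, expects the share of eligible patients given addiction treatment to rise from 15% "to 26% during the evaluation phase and 33% during the maintenance phase". The calculation uses "15% control vs. 26% intervention" with "power 90% and Type I error (alpha) of 0.05". It reaches 592 patients for a parallel design, a stepped wedge design effect of 0.63, and 375 patients (94 per clinic). At least 300 eligible patients per clinic are assumed.

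From this the section concludes that power is also adequate for maintenance "and for the other quantitative analyses proposed in Aims 2 and 3".

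Those other analyses include Aim 3, which Section V, 1. Statement of Purpose limits to treatment-eligible patients: "To evaluate the impact of Implementation Facilitation on ART receipt, viral suppression, VACS Index, and retention in HIV care". They also include Aims 2a and 2b, organizational and provider readiness, which are measured in staff. On staff numbers, Section V, 4. Subject Population says: "We will also enroll an estimated 240 staff (clinicians and administrators) across the four sites". The overview of the effectiveness evaluation in Section V lists the ORCA, the change rulers and the HIV outcomes as secondary.

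**The concern.** Power belongs to a particular outcome, effect size and sample. An 11-point difference in one binary process measure says nothing about a different binary outcome with a different base rate and a smaller expected effect, about a continuous score, or about a different set of respondents. The clause is the only power justification offered for Aims 2a, 2b and 3.

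For the HIV outcomes there is a specific reason to expect a smaller effect. If the intervention changes viral suppression mainly by getting more patients treated, the change across all eligible patients is the added uptake multiplied by the effect in those newly treated. That product can be far below 11 points.

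The risk lies in interpretation. With a statement of adequate power on file, a non-significant Aim 3 result is easily read as showing that facilitation does not affect HIV outcomes.

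**Working it through.** **1. The plan's own figures.** A two-sided 5% test of 15% versus 26% at 90% power needs 281 per arm without continuity correction and 299 with it. The plan's 296 per arm (592) is in line with the corrected figure. The stepped wedge design effect with n = 300, ρ = 0.01, k = 4, b = 1, t = 1 is

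[1 + ρ(ktn + bn − 1)] / [1 + ρ(ktn/2 + bn − 1)] × 3(1 − ρ) / [2t(k − 1/k)]
= (1 + 0.01 × 1499) / (1 + 0.01 × 899) × 2.97 / 7.5 = 0.634.

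592 × 0.634 = 375, or 94 per clinic. The figures reproduce; the error is in what is inferred from them.

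**2. Effective size for another patient outcome, with the same design effect.** 375 patients correspond to 296 per arm. The assumed minimum of 4 × 300 = 1,200 corresponds to 1,200 / 0.634 / 2 = 947 per arm.

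**3. Effect on viral suppression.** The documents give no suppression rate and no effect of addiction treatment on suppression. Assumptions:
- a share s = 70%, 80% or 90% of eligible patients is suppressed in the control period;
- facilitation acts through added treatment;
- newly treated patients resemble all eligible patients;
- every newly treated, unsuppressed patient becomes suppressed.

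Then d = added uptake × (1 − s). Added uptake is 11 points in evaluation and 33 − 15 = 18 in maintenance. (The text says 19.)

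Power = Φ(d / √[(p₁q₁ + p₂q₂)/n] − 1.96), with p₁ = s, p₂ = s + d, q = 1 − p, and n per arm from step 2.

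| Phase | s | d (points) | Power, 375 patients | Power, 1,200 patients |
|---|---|---|---|---|
| Evaluation | 70% | 3.3 | 14% | 36% |
| Evaluation | 80% | 2.2 | 10% | 23% |
| Evaluation | 90% | 1.1 | 7% | 13% |
| Maintenance | 70% | 5.4 | 32% | 75% |
| Maintenance | 80% | 3.6 | 21% | 53% |
| Maintenance | 90% | 1.8 | 12% | 28% |

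With 19 points instead of 18, the last column for maintenance becomes 80%, 58% and 30%.

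**4. Without assuming a mechanism.** Starting from 80% suppressed, the smallest increase detectable at 90% power is about 9.5 points with 375 patients and 5.6 points with 1,200. The plan states no expected effect to set against these.

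**5. Sensitivity.** With s = 60%, 1,200 patients and maintenance, d = 0.18 × 40 = 7.2 points and power is about 90%. With 80% suppressed overall but only 50% among the newly treated, d is 5.5 points (evaluation) and 9.0 points (maintenance). Power is then 43% and 86% with 375 patients, and 89% and over 99% with 1,200.

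**6. Staff scores (Aims 2a and 2b).** 240 staff with the plan's design effect give 240 / 0.634 / 2 = 189 per arm. The detectable difference at 90% power is (1.96 + 1.28) × √(2/189) = 0.33 SD. No SD or target difference is stated, so this cannot be judged as enough or too little.

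**The case against.** The strongest objection is that the Aim 3 analysis, as written in Section V, 11. Statistical Considerations, relates HIV outcomes to receipt of addiction treatment. That treated-versus-untreated contrast is not diluted by the uptake increase. Ignoring clustering, with 26% treated and 70-80% at goal among the untreated, a 10-point difference has 48-63% power with 375 patients and 94-99% with 1,200. This is correct. But that comparison is not randomised, it is not the impact of facilitation that Aim 3 names, and the plan gives no calculation for it either.

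Other points also stand. The 375 is a calculated requirement, not a cap: outcomes come from medical records, and more eligible patients may be available. The calculation here, like the plan's, treats the periods as cross-sectional. The plan notes that a stable cohort would help through within-patient correlation, though it gives no value. The outcomes are labelled secondary, and 95% confidence intervals are already promised for the odds ratios in Aim 3.

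Three stronger readings are tempting and not supported:
- A reader might conclude that power for HIV outcomes simply is 7-14%. That is the least favourable set of results, for one outcome, one phase and the smaller sample, under assumed rates.
- A reader might infer that the trial could not detect even the largest possible effect. Step 5 shows plausible inputs at which it could.
- A reader might set 60 staff per clinic (240 / 4) against the 94 required. The 94 belongs to a binary patient outcome and is no yardstick for continuous staff scores.

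None of these points supplies the missing basis for the blanket clause.

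**Conclusion.** The concern holds as a defect of inference. The power statement for the remaining analyses of Aims 2 and 3 rests on a calculation for a different outcome, and the inputs needed to check it are absent. The arithmetic for the primary outcome is not in question.

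The size of any shortfall depends on assumptions. For the impact of facilitation on viral suppression, no combination in the table of step 3 reaches the plan's 90%, and most fall well short. Power is higher if fewer patients are suppressed at the start, if newly treated patients are less often suppressed than the rest, or if more patients are eligible. It is lower if treatment does not bring every unsuppressed patient to goal. The documents do not say that facilitation acts only through added treatment, so the table is a demonstration that adequacy cannot be presumed, not an estimate of the trial's power. For the staff outcomes, adequacy is unsupported, not shown to be lacking.

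**What to change.** In Adequacy of sample size, delete "and for the other quantitative analyses proposed in Aims 2 and 3". In its place:
- Give a short table with the smallest difference detectable at 90% power for viral suppression, ART receipt, retention, VACS Index, ORCA and the change rulers. Use the expected numbers of eligible patients and of staff, with the base rate or SD and the intracluster correlation stated for each.
- For Aim 3, give this for the effect of facilitation and, separately, for the treated-versus-untreated association.
- State that these secondary analyses are not separately powered, that all are reported as estimates with 95% confidence intervals, and that a non-significant result is not evidence of no effect.

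The cost is a wording change and one table. No patients, endpoints or data collection are added. The drawback is that the stated power becomes less favourable.

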#### Pre-implementation and serial assessments

**Organizational Readiness:** We will use the ORCA to measure factors impacting the provision of addiction treatments. This 15-minute survey is based on the PARIHS framework and asks the respondent to rate local factors related to evidence, context and facilitation on a 5-point Likert scale from strongly disagree to strongly agree. Facilitation questions will be omitted from the pre-implementation assessment since this part of the intervention and will not have taken place.

**Provider Readiness:** We will use change rulers, among appropriate providers, for each of the medications and counseling to assess readiness to provide each medication and counseling intervention. The change rulers will independently assess, on a 0-10 scale each provider’s: 1) confidence to prescribe/provide the intervention, 2) readiness to prescribe/provide the intervention and 3) commitment to prescribe/provide the intervention. Stage of change assessments have been validated and have been used in the field of addiction and mental health to assess readiness to adopt evidence-based treatments.

**Addiction Treatment Eligibility:** We will work with each site to incorporate screening for smoking and use of the AUDIT-C, NIAAA single question screen or NIDA-MED ASISST. The NIDA-MED ASISST and NIAAA screen have good operating characteristics for both alcohol and drug use disorders in medical settings. We will use electronic medical records to identify addiction treatment eligible patients based on ICD-9 diagnoses for current (or in remission, at risk for relapse) substance use disorders, positive NIDA-MED ASISST or for tobacco - smoking 5 or more cigarettes/day and alcohol - AUDIT-C > 3, positive NIAAA screen.

**Provision of Addiction Treatments:** We will use the electronic medical record to identify prescriptions for each of the target medications in the surveillance period. We will use CPT codes to determine whether specific counseling therapies were provided.

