**Table 3. Site Descriptions, Current Need and Provision of Addiction Treatments**

Site	Miriam Immunology Center	Boston Medical Center	Hartford Hospital	Downstate
Number of HIV-infected receiving care	1600	1200	500	1200
Number with untreated Tobacco Use Disorder	400	300	200	425
Number receiving on-site medication for tobacco use disorder (bupropion, NRT, varenicline)	140	Unknown	75	110
Number receiving on-site counseling for tobacco use disorder	Unknown	Unknown	50	7
Number with untreated Unhealthy Alcohol Use	100	200	75	240
Number receiving on-site medication for unhealthy alcohol use (naltrexone, acamprosate, disulfiram)	0	16	0	0
Number receiving on-site counseling for unhealthy alcohol use	Unknown	16	0	100
Number with untreated Opioid Use Disorder	80	100	80	100
Number receiving on-site medication for opioid use disorder (buprenorphine, naltrexone)	32	50	0	4
Number receiving on-site counseling for opioid use disorder	32	50	0	7

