### **Evaluating the Effectiveness of the Implementation Facilitation (Aim 2 and Aim 3)**

#### Overview

We will use a stepped wedge design (Table 4) to evaluate the effect of the Implementation Facilitation on the outcomes. In a stepped wedge design, clinics are randomly assigned to time cohorts and then followed prospectively to determine their outcome status. Stepped wedge designs are increasingly used to promote the implementation of evidence-based practice and are appropriate for evaluating interventions where there is evidence that the intervention is likely to be beneficial and when practical considerations require sequential deployment of an intervention. We will have three phases of six-months each: 1) a pre-implementation control period, 2) a post-intervention evaluation period, and 3) a maintenance period. The proportion of eligible patients in each time period who receive at least one addiction treatment will be assessed and the effect of the intervention will be evaluated by comparing pre-implementation to evaluation and maintenance periods. This will allow us to assess the short and long-term (maintenance) impact of Implementation Facilitation.

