**Analysis for Aim 3:** These analyses will be restricted to patients diagnosed with a tobacco, alcohol or opioid use disorder. ART receipt will be defined as at least 180 days of three concurrent antiretroviral agents in the 6-month interval based on prescriptions in the electronic medical record. Viral suppression, will be defined as HIV RNA <200 copies/mL at last test closest to the time of data extraction, consistent with Department of Health and Human Services (DHHS) guidelines. Although current limits of detection are lower, this cutoff allows for low-level “blips” that have no clinical significance. The VACS Index will be evaluated based on most recent values at the time of data extraction. VACS Index score will be treated as a continuous variable. Retention in HIV care, per DHHS guidelines uses a 24-month measurement period. It is defined as at least one HIV medical care visit in each 6-month period, with a minimum of 60 days between the first medical visit in the prior 6-month period and the last medical visit in the subsequent 6-month period. This measure has good agreement with the Institute of Medicine indicator for retention in care and is an independent predictor of mortality. We will evaluate whether patients have had at least 1 visit in the 6-month period prior to time of data extraction. These analyses will be adjusted for demographics (age, gender), and presence of psychiatric diagnosis (anxiety, major depression, severe mental illness). We will use descriptive statistics to characterize addiction treatment eligible patients overall and by substance at baseline and examine changes at each interval. We will then examine each of these HIV-related outcomes at the 6-month intervals of control, evaluation and maintenance phases based on the provision of addiction treatment. We will determine the association between provision of addiction treatment, including benzodiazepines and outcomes with the MIXED models procedure repeated measures and generalized estimating equations (GEE) to account for repeated measures for dichotomous outcomes. We will adjust for fixed demographics, substance use disorder and psychiatric diagnoses. We will describe the association with odds ratios and 95% confidence intervals. For continuous outcomes, we will use multivariable linear regression with GEE with similar adjustment.

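### Any recorded prescription of a target drug counts as addiction treatment, so bupropion taken for depression is scored as provision in every phase

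*Combined protocol and SAP*

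**What the plan says.** The primary outcome is a proportion that needs one treatment per patient. The Overview of the effectiveness evaluation says: "The proportion of eligible patients in each time period who receive at least one addiction treatment will be assessed".

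The paragraph on provision of addiction treatments, under Pre-implementation and serial assessments, gives the numerator. For drugs: "We will use the electronic medical record to identify prescriptions for each of the target medications in the surveillance period". For counseling: "We will use CPT codes to determine whether specific counseling therapies were provided". No indication, linked diagnosis or eligible substance is mentioned.

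Table 3 shows that bupropion is a target drug; its row label begins "Number receiving on-site medication for tobacco use disorder (bupropion, NRT, varenicline". A patient can become eligible through tobacco (for example, "smoking 5 or more cigarettes/day"), alcohol or opioids.

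Table 5 extracts medication use and psychiatric diagnoses at baseline, 6 months and 12 months. The analysis section uses the psychiatric data only as an Aim 3 covariate, "presence of psychiatric diagnosis (anxiety, major depression, severe mental illness". They play no part in deciding who was treated.

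**The concern.** Bupropion has two common uses, and the rule cannot tell them apart. (The second use is general pharmacological knowledge; the protocol does not mention it.) A smoker on long-term bupropion for depression meets the numerator in every phase, whatever IF does. As written, so does a patient eligible only through alcohol or opioids who takes bupropion for mood.

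Three things are at stake:

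- The reported provision rate, which is the descriptive result of Aim 2c, is too high in every phase.
- The contrast between phases is diluted. The patient random effect does not remove this, because such a patient contributes no change between phases.
- Aim 3 relates provision of addiction treatment to HIV outcomes. These patients enter as exposed, so an association could partly reflect depression care.

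The tobacco drugs are where most recorded medication treatment lies. In Table 3 they account for 140 + 75 + 110 = 325 of the known on-site medication recipients. Alcohol adds 16 and opioids 32 + 50 + 4 = 86, for a total of 427, so tobacco is 76%. One site's tobacco figure is unknown, patients may be counted twice, and the table does not split bupropion from the other tobacco drugs.

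**Working it through.** **Inputs from the plan (Adequacy of sample size).** The anticipated rates run "from a baseline of 15% of eligible patients (Table 3) to 26% during the evaluation phase", with "power 90% and Type I error (alpha) of 0.05". The unadjusted size is 296 per arm (592). There are at least 300 eligible patients in each of 4 clinics, intracluster correlation 0.01, k = 4, b = 1 and t = 1. The stepped-wedge design effect is 0.63 and the adjusted total 375.

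**Assumed input.** f is the share of otherwise untreated eligible patients who hold a bupropion prescription for depression. The documents give no value. I show 2%, 5% and 10%.

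**Step 1: reproduce the plan.** A two-sided test of 15% against 26% at 90% power, with continuity correction, needs 299 per arm (598), within about 1% of 592. The design effect is

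[1 + 0.01(1200 + 300 − 1)] / [1 + 0.01(600 + 300 − 1)] × 3(0.99) / [2(4 − 1/4)] = (15.99 / 9.99) × (2.97 / 7.5) = 0.634,

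and 592 × 0.634 = 375. The plan's figures hold.

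**Step 2: effect of the rule when f is the same in all phases.** The observed rate is p + (1 − p)f. The control rate rises by 0.85f and the evaluation rate by 0.74f, so the difference is 0.11(1 − f). The false-positive share of control-phase treated patients is 0.85f / (0.15 + 0.85f).

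| f | Control | Evaluation | Difference (points) | Odds ratio | False-positive share, control |
|---|---|---|---|---|---|
| 0 | 15.0% | 26.0% | 11.0 | 1.99 | 0 |
| 2% | 16.7% | 27.5% | 10.8 | 1.89 | 10% |
| 5% | 19.3% | 29.7% | 10.5 | 1.77 | 22% |
| 10% | 23.5% | 33.4% | 9.9 | 1.63 | 36% |

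**Step 3: power.** At the parallel-group reference of 296 per arm (two-sided 0.05, pooled null variance), power is 91.4% at f = 0 and 88.7%, 84.2% and 76.2% at the three values of f. That is not the size of this trial. With continuity correction, the size for 90% power is 328, 373 or 455 per arm. Doubling, multiplying by 0.634 and dividing by 4 gives about 104, 118 or 144 patients per clinic, against 95 at f = 0 by the same formula. All are well below 300. With 4 × 300 = 1,200 patients, the parallel-group equivalent is 1200 / 0.634 / 2 ≈ 947 per arm, and power at f = 10% is about 99.8%.

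**Step 4: if the planned 15% already contains such prescriptions.** The true control rate is then (0.15 − f)/(1 − f). A true gain of 11 points still appears as 11(1 − f), but from an observed 15%. Power at 296 per arm is 90.4%, 88.8% or 85.6%.

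**Step 5: if f differs by phase.** The observed difference is 0.11 + 0.74f₁ − 0.85f₀, where f₀ is the control share and f₁ the exposed share. It exceeds 11 points once f₁ > (0.85/0.74)f₀ = 1.15f₀. From f₀ = 5%, that means f₁ above about 5.7%.

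**The case against.** The strongest reply is that the plan never says a prescription counts whatever its indication. The rule stands under a heading about addiction treatment, and the Table 3 label ties the tobacco drugs to tobacco use disorder. That shows the intent. But nothing in the extraction rule carries the intent through, and a programmer at any of four clinics who follows the text would count every bupropion order.

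A reader might infer from the 76% figure that the trial is underpowered. The documents do not support that. The 296 per arm is only the unadjusted reference, and on the plan's own design effect and 300 patients per clinic the loss has little practical effect.

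A reader might also infer that the bias must run toward no effect. That holds only if antidepressant prescribing is unrelated to IF; Step 5 shows how small a rise would reverse it.

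It is fair to say that f is undocumented, that a covariate list gives no prevalence of depression, and that at f of a few percent the dilution is modest. It is also fair that Aim 3 already adjusts for psychiatric diagnosis. This helps, but it does not separate treated from untreated depression among patients who share the diagnosis.

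Finally, a primary rule that requires the order to be linked to a tobacco diagnosis could do harm. Table 5 lists no order-level indication. The provider education component of IF also covers efficient use of the electronic record, so better documentation alone could raise measured treatment after IF. This objection stands and shapes the fix.

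**Conclusion.** The point holds as a misclassification built into the numerator rule. Followed as written, the rule scores bupropion for depression as addiction treatment in every phase and as exposure in Aim 3.

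Under equal f across phases, the Aim 2c difference is diluted by a factor (1 − f): about 0.2 to 1.1 points of the planned 11 over f = 2% to 10%. The effect on the reported provision rate is larger, since between a tenth and a third or more of control-phase treated patients could be false positives over the same range. These sizes rest on an assumed f, on the 15% excluding such prescriptions, and on IF not changing antidepressant prescribing. The trial is not invalidated and power is not the issue. What remains is a diluted contrast, an inflated provision rate and a mixed exposure in Aim 3, all of which can be examined cheaply.

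**What to change.** In the paragraph on provision of addiction treatments, state that bupropion counts as tobacco treatment only in patients eligible through tobacco, and apply that rule identically in control, evaluation and maintenance.

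For Aim 2c and Aim 3, prespecify two sensitivity analyses: one that does not count bupropion in patients with a depression diagnosis, and one that leaves bupropion out of the numerator altogether. Do not make order-to-diagnosis linkage the primary rule.

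The cost is one line in the extraction program and two reruns, using medication, substance use disorder and psychiatric diagnosis fields that Table 5 already lists at every phase. The downside is that the first sensitivity analysis misses bupropion given for smoking to patients with depression, and the second misses all bupropion given for smoking. Each should therefore be reported beside the primary result and not in place of it.
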